### **Simulation Scenarios:**

The same scenarios were used for the baseline and final assessments for both groups and were prepared from the Textbook of Neonatal Resuscitation 7th edition of the American Association of Pediatrics (Nimbalkar et al., 2015). Here's below the four simulation scenarios are as follow:

- a) A term pregnant lady having a history of gestational diabetes. After the birth of the baby, it was found that the baby is not breathing.
- b) An expecting mother having a history of placenta abruption. After birth during the initial evaluation, the baby was found gasping 1 minute after birth.
- c) A term pregnant woman presenting with a road traffic accident. After birth, it was found that the baby is not crying and having poor muscle tone.
- d) The baby has just been born. The baby was not breathing with a heart rate of less than 60 and appear cyanotic.

For the assessment of all steps of resuscitation skill, only newborn scenarios were added for the maximal exposure of student nurses to all the steps of resuscitation (Lee, Brown, Bender, Machan, & Overly, 2012). The student performance was assessed through a neonatal resuscitation checklist (Abusaad & Ebrahem, 2015). All the students gave a maximum time of 10 minutes to perform all the steps of resuscitation. However, students can finish it earlier than 10 minutes if all steps had been followed. A lab assistant was present there and make a video recording of all students' performance to validate the observations and scoring. For the maintenance of confidentiality, the videos were deleted after corroboration (Delgado et al., 2017).

**Data Collection Tools:** The following tools were used for data collection.

**1. Demographic Data Tool:**

The demographic form contains information regarding age, year of the profession, primary language, marital status, Division, previous exposure to neonatal resuscitation.

**2. Skill Assessment Tool:**

Neonatal resuscitation checklist: A 30 items checklist will be used. Each of the correct actions was graded as 1=yes and for wrong action 0=no. The non-technical skills were measured through a 9-item checklist on a 5-point Likert scale. The Cronbach's  $\alpha$  of 0.719 and the intra-rater reliability of 0.885 were reported for the neonatal resuscitation checklist (Rovamo et al., 2011).

**3. Knowledge Tool:**

Knowledge will be tested through 17 items of multiple-choice questions adopted from the Knowledge Questionnaire (Mileder et al., 2019).

**4. Self-efficacy Tool:**

Self-efficacy for Neonatal Resuscitation (SENR): The structure of the questionnaire was grounded on Bandura's (1977) Self-Efficacy Scale (SES). The SENR instrument is a 23-item scale that measured nursing students' perception of confidence in their capabilities in neonatal resuscitation. All SENR items were valued on a 10-point Likert scale. The SENR established good internal consistency with a Cronbach alpha value of 0.93 was reported (Nyiringango, 2019). The final score will be calculated by averaging the items from the subscales and thereafter averaging all 24 items for the total SENR score.

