### **Study Variables:**

#### **Independent Variable:**

1. The Educational intervention is the independent variable was measured either through LSPPDM pedagogy, a six-step method, and a traditional 2 step method.

**Dependent Variable:** The dependent variable were:

1. Knowledge was measured through 17-item multiple-choice questions adopted from Knowledge Questionnaire (Milededer, Gressl, Urlesberger, & Raith, 2019).
2. Self-efficacy measured through a 23-item scale called the Self-Efficacy for Neonatal Resuscitation Instrument (Nyiringango, 2019).
3. Skill was measured through a 30 item checklist for measuring technical skills and the non-technical skills were measured through a 9-item checklist on a 5-point Likert scale in neonatal resuscitation (Rovamo, Mattila, Andersson, & Rosenberg, 2011).

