## **DATA ANALYSIS PLAN**

The data were analyzed by using Statistical Package for the Social Sciences (SPSS) version 25. Mean and SD were given for age, knowledge score, skill score and self-efficacy score. Frequency and percentage were given for education, language, marital status, division in previous result, residential area and previous neonatal resuscitation exposure. Both groups tested for homogeneity in general and resuscitation specific characteristics using  $\chi^2$  -test, and t-test. Independent sample t test was used to compare the mean age, knowledge score, skill score and self-efficacy score between both groups. Paired t test was used to compare the pre and post education knowledge, skill and self-efficacy score in both groups. Chi square / Fisher's exact test was used to compare the education level, language, marital status, division in previous result, residential area and previous neonatal resuscitation exposure between both groups. A p-value  $\leq$  0.05 was taken as significant.

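### Does the mismatch between 23 and 24 SENR items leave the self-efficacy score undefined?

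*Combined protocol and SAP*

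**What the plan says.** Under Study Variables, in the list of dependent variables, the plan states: "Self-efficacy measured through a 23-item scale called the Self-Efficacy for Neonatal Resuscitation Instrument". The Self-efficacy Tool section under Data Collection Tools repeats the count ("The SENR instrument is a 23-item scale") and gives the response format: "All SENR items were valued on a 10-point Likert scale". The same section ends with the scoring rule, which obtains the final score by "averaging the items from the subscales and thereafter averaging all 24 items for the total SENR score".

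The Data Analysis Plan uses that score in three ways. It is summarised ("Mean and SD were given for age, knowledge score, skill score and self-efficacy score"), compared between groups ("Independent sample t test was used to compare the mean age, knowledge score, skill score and self-efficacy score between both groups") and compared within groups ("Paired t test was used to compare the pre and post education knowledge, skill and self-efficacy score in both groups"). The documents do not list the items, name the subscales, give subscale sizes or account for a 24th item.

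**The concern.** The instrument is twice given 23 items, and its total is then defined over 24. Nobody can average 24 items from a 23-item form, and nothing in the documents shows which number is the slip. Self-efficacy supports the third objective and hypothesis c, and this sentence is the only definition of its score.

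Two things could be at stake. If 24 were used as a fixed divisor for 23 responses, reported self-efficacy would be too low. If the form really had 24 items and only 23 were scored, totals would shift by an amount that differs between students. The sentence also mentions subscale averages first, so one might ask whether the total is a mean of items or a mean of subscale means.

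**Working it through.** **Inputs.** Item count 23 (Study Variables; Self-efficacy Tool). Item count 24 (scoring sentence, Self-efficacy Tool). Ten-point items (Self-efficacy Tool); the end points are not given, so 1 to 10 coding is assumed. Independent and paired t tests (Data Analysis Plan).

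**The plan's own figure.** The 24 cannot be reproduced. The stated count is 23, the difference is 24 − 23 = 1, and there are no subscale sizes from which 24 could be built up.

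**Case 1: the recorded item columns are averaged.** With k items on the form, total = (sum of the k responses)/k. This is right for k = 23 and for k = 24. The digit in the text plays no part.

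**Case 2: 23 responses are summed and divided by a fixed 24.** Every score is multiplied by c = 23/24 = 0.958, so it is 1 − 0.958 = 0.042, or 4.2%, too low.

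- Maximum score: 10 × 23/24 = 9.58.
- Illustrative mean of 7.00: 7.00 × 23/24 = 6.71.
- Illustrative group difference of 1.00: 1.00 × 23/24 = 0.96.

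The SD is also multiplied by c. In the independent-samples test, t = (difference in means)/(SE of the difference), and both parts carry the factor c, so it cancels. In the paired test, t = (mean change)/(SD of change/√n), and c cancels again. Neither p-value changes.

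**Case 3: the form has 24 items and one is left out.** Let m be a student's mean on the 23 scored items and x the response to the omitted one. The correct total is (23m + x)/24, so the error is (x − m)/24 in size. With 1 to 10 coding the largest possible value is (10 − 1)/24 = 0.375 points for one student. This is not a constant rescaling, so the tests could move.

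For the group difference, the error is (Δx − Δm)/24, where Δx and Δm are the group differences on the omitted item and on the mean of the others. If those differ by 1 point (assumed), the estimated difference moves by 1/24 = 0.04 points.

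**The subscale wording.** The second averaging in the scoring sentence is applied to items, not to subscale scores. Its natural reading is that each subscale score is a mean of its items and the total is the mean of all items. A mean of subscale means would need words that are not there.

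**Sample size.** The calculation in Methods uses skill means of 8.71 and 7.03 with SDs of 1.48 and 1.33. Self-efficacy does not enter it, so the item count cannot affect it.

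**The case for a change.** The best argument for a change is that an outcome behind one of three hypotheses should have a scoring rule that a second analyst can apply without guessing. The rule appears once, it conflicts with two other statements, and correcting it would take only a look at the form and one edited digit. The claim that the tests are safe also has a limit: it holds in Cases 1 and 2 but not in Case 3. If the form had 24 items, one could also ask whether the quoted Cronbach alpha of 0.93 belongs to that version.

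Much of this stands. The contradiction is in current text, in complete sentences, and does not look like a product of the PDF conversion. The documents do not settle which count is correct, and invariance of the t tests cannot be claimed for every conceivable error.

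It does not show that the analysis would go wrong. Case 2 needs a hard-coded divisor, whereas the plan speaks of averaging and names SPSS, where a mean is taken over the item variables. Case 3 needs someone to discard a completed item although the rule says to use all of them. On either form, the word governing the calculation is the one that calls for every item, and the analyst has the form in hand. The alpha is a figure reported for the instrument and is not used in any planned comparison.

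**Conclusion.** The count is inconsistent, most plausibly through a typing slip, and the plan needs no change because of it. An analyst following the rule would average the items on the form used and obtain the correct score, so aligning the digits would not alter any planned estimate or test.

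The sizes are small even if something did go wrong: 4.2% on the descriptive scale with unchanged p-values under a fixed divisor of 24, and at most 0.375 points for any one student if a real 24th item were dropped.

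This rests on three assumptions: the total is the mean of all items, as the sentence most naturally reads; one scoring method is used for all students at both time points; and items are coded 1 to 10, which matters only for the 0.375 bound and for the maximum of 9.58.

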## **DATA ANALYSIS PLAN**

The data were analyzed by using Statistical Package for the Social Sciences (SPSS) version 25. Mean and SD were given for age, knowledge score, skill score and self-efficacy score. Frequency and percentage were given for education, language, marital status, division in previous result, residential area and previous neonatal resuscitation exposure. Both groups tested for homogeneity in general and resuscitation specific characteristics using  $\chi^2$  -test, and t-test. Independent sample t test was used to compare the mean age, knowledge score, skill score and self-efficacy score between both groups. Paired t test was used to compare the pre and post education knowledge, skill and self-efficacy score in both groups. Chi square / Fisher's exact test was used to compare the education level, language, marital status, division in previous result, residential area and previous neonatal resuscitation exposure between both groups. A p-value  $\leq$  0.05 was taken as significant.

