## METHODS

### Study design and Setting

A Single-blind Randomized Control Trial adheres to the CONSORT guiding principle (Figure 1).

The setting was the college of Nursing, Allama Iqbal Medical College, Lahore Pakistan, a specialized tertiary level educational center in the public sector that offers (2 & 4year) graduation in nursing and 1-year post basic specialization in various disciplines. The participants were 3rd and 4th professional B.sc nursing students (4 years) enrolled in the current year of 2020-2021.

**Duration of Study:** October 2020 to March 2021.

**Sample Size:** The sample size is calculated using the *OpenEpi* software (Kim & Ahn, 2019b) The calculated sample size is 24 (12 in each group). This sample size is small to perform the statistical test with good efficacy. So, 30 in each group will be taken,  $n = 60$  (30 in each group). After adding a 20% dropout rate the final sample size will become 72 (36 in each group).

The sample size is calculated using the following information and formula;

$$n = \frac{(Z_{1-\beta} + Z_{1-\alpha/2})^2 + (\delta_1^2 + \delta_2^2)}{(\mu_1 - \mu_2)^2}$$

$\alpha$	5%
$1 - \alpha$	95%
$1 - \beta$	80%
$Z_{1-\alpha/2}$	1.96
$Z_{1-\beta/2}$	2.58
$\mu_1$ Expected mean in Skill in intervention Group (LSPPDM Pedagogy)	8.71(Kim & Ahn, 2019b).

$\mu_2$ Expected mean in Skill in Control (Traditional)	7.03(Kim & Ahn, 2019b).
$\delta_1$ Expected standard deviation in Skill Intervention (LSPPDM Pedagogy)	1.48(Kim & Ahn, 2019b).
$\delta_2$ Expected standard deviation in Skill in Control (Traditional)	1.33(Kim & Ahn, 2019b).
n Expected sample size in each group	24

Sample Size For Comparing Two Means			
Input Data			
Confidence Interval (2-sided)	95%		
Power	80%		
Ratio of sample size (Group 2/Group 1)	1		
Group 1		Group 2 Difference*	
Mean	8.71	7.03	1.68
Standard deviation	1.48	1.33	
Variance	2.1904	1.7689	
Sample size of Group 1	12		
Sample size of Group 2	12		
Total sample size	24		

**Sampling Technique:** Simple random sampling.

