**Exclusion Criteria:**

The nursing students were excluded who:

- Were on leave from that period
- Had already received any educational training on neonatal resuscitation.
- Working as Nursing Assistants in Clinical Setting.

[figure not shown]

Figure 1. Consort Diagram

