## **DATA COLLECTION PROCEDURE**

### **Recruitment:**

The list of all nursing students in the 3rd and 4th professional was developed and the participants were recruited through simple random sampling. Initially, 62 participants (31 in each group) meet the inclusion criteria. Two participants were dropped in the follow-up for personal reasons one was not attending the full course of intervention and the other was absent on the days of evaluation. Thus, yielding a total of 60 participants (30 in each group).

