### **Randomization and Allocation:**

The students allocated from each professional in traditional group and Pedagogy group through the Lottery method (Moon & Hyun, 2019). The difference in the professional year was overcome through equal distribution of each professional student in both groups. Allocation of participants was concealed using envelop method.

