### **Methods for Collection of Data:**

Two facilitator evaluators were trained regarding the scoring of each scale in a two-hour workshop before data collection (Kirkpatrick, Cantrell, & Smeltzer, 2019). The data was collected at two points in time in the Simulation lab.

- 1st-time data was collected as a pre-test before the educational intervention.
- The 2nd-time data was collected after 6 weeks of educational intervention.

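### The between-group test for all three outcomes is an unadjusted t-test with no stated time point, although the pre-test and the balancing factor (professional year) are available as covariates

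*Combined protocol and SAP*

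**What the plan says.** The Data Analysis Plan states: "Independent sample t test was used to compare the mean age, knowledge score, skill score and self-efficacy score between both groups". This is the only between-group test of the three outcomes. The sentence does not say whether pre-test, post-test or change scores are compared. It also covers age, a baseline variable, so the context does not settle the question. Post-test is the natural reading.

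Baseline information enters the plan in two other places, and neither adjusts the outcome comparison:

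- Balance checks: "Both groups tested for homogeneity in general and resuscitation specific characteristics using" chi-square and t-tests.
- Paired t-tests of pre against post scores, which are comparisons over time and not between groups.

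The covariates themselves exist. Under Methods for Collection of Data, the first round of "data was collected as a pre-test before the educational intervention". Under Randomization and Allocation, "The difference in the professional year was overcome through equal distribution of each professional student in both groups". Professional year is also recorded: "The demographic form contains information regarding age, year of the profession, primary language, marital status" and other items. No ANCOVA, regression or stratified analysis appears anywhere in the document.

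**The concern.** The design treats professional year as important enough to balance, and it measures each outcome before teaching starts. The between-group analysis then uses neither. Two things follow.

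- **Precision.** If pre-test scores or year predict post-test scores, the unadjusted interval is wider than it need be. If year is prognostic, the t-test is also slightly conservative, because balancing removes year from the true variance of the difference while the t-test leaves it in the estimated variance.
- **Ambiguity.** A post-test t-test and a change-score t-test are different analyses with different precision. Leaving the choice open allows it to be made after the data are seen.

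The objectives and hypotheses are between-group comparisons of all three outcomes, but the sample-size calculation covers skill only. Knowledge and self-efficacy therefore have no stated margin of power to give away.

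**Working it through.** **Inputs from the documents.** Skill means 8.71 and 7.03 (difference 1.68), SDs 1.48 and 1.33, two-sided alpha 5%, power 80% (sample-size section); 30 per arm analysed (Recruitment).

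**Assumed, because the documents do not give them.** Pre/post correlation r = 0.1 to 0.7; a year effect of zero or 10% of post-test variance; an effect of 0.5 SD for knowledge and self-efficacy; year split 15+15 in each arm; independent students.

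**1. The plan's own figure.** With the product form of the formula, n per group = (1.960 + 0.842)² × (1.48² + 1.33²) / 1.68² = 11.01, rounded up to 12, so 24 in total, as stated. It rests on an unadjusted comparison. Pooled SD = √[(1.48² + 1.33²)/2] = 1.407, so the planned difference is 1.68/1.407 = 1.194 SD. At 30 per arm the noncentral-t power for that difference is 99.5%.

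**2. ANCOVA against the post-test t-test, no year effect.** The t-test SE is √(2/30) = 0.258 SD. For the model with group, pre-test and year, the expected variance inflation from chance pre-test imbalance is 1 + 1/55, so

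SE ratio = √[(1 − r²)(1 + 1/55)].

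Power uses the noncentral t with 58 df (t-test) or 56 df (ANCOVA). The half-widths are mean 95% CI half-widths on the planning skill scale (SD 1.407) from simulation, 40,000 trials per setting.

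| | t-test | r = 0.1 | r = 0.3 | r = 0.5 | r = 0.7 |
|---|---|---|---|---|---|
| SE ratio | 1 | 1.004 | 0.963 | 0.874 | 0.721 |
| Mean half-width | 0.724 | 0.727 | 0.697 | 0.633 | 0.522 |
| Trials where ANCOVA is wider | – | 66% | 20% | 1% | 0% |
| Power, 0.5 SD effect | 48% | 47% | 51% | 59% | 75% |
| Difference detectable with 80% power (SD) | 0.736 | 0.739 | 0.709 | 0.643 | 0.530 |
| Power, skill at 1.68 | 99.5% | 99.5% | 99.7% | 99.9% | >99.9% |

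Break-even on the SE: (1 − r²)(56/55) = 1, so r = √(1/56) = 0.134. Allowing for the lost degrees of freedom in the critical value, it is 0.139 for the half-width.

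**3. Year explains 10% of post-test variance** (r is now the correlation within year). Residual variance falls by a further factor of 0.9. Mean ANCOVA half-widths are 0.69, 0.66, 0.60 and 0.50 against about 0.725 for the t-test, a gain even at r = 0.1.

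The t-test's true size: the variance of the difference is 0.9 times nominal, while the expected pooled variance is 0.9 + 0.1 × 30/29 = 1.003. The critical value 2.002 therefore acts as 2.002 × √(1.003/0.9) = 2.114, which on 58 df gives 3.9%. Simulation gave 3.7% to 3.9% for the t-test and 4.8% to 5.1% for ANCOVA.

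**4. If change scores were meant** (equal pre and post SDs). SE ratio to the post-test t-test = √[2(1 − r)] = 1.342, 1.183, 1.000, 0.775. The half-width is 0.98, 0.86, 0.73, 0.56, wider than ANCOVA at each r shown.

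**The case against.** The strongest reply is that the t-test is a pre-named test that omitting covariates does not invalidate, that power for the one outcome the trial was sized on is ample, and that this is a preference about efficiency with an unknown pay-off. Much of that is fair.

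- **The gain is not known.** No correlation, year effect or effect size for knowledge or self-efficacy is given. A weak correlation is plausible, because students are excluded who "Had already received any educational training on neonatal resuscitation", so pre-test scores may cluster low. At r = 0.1 with no year effect, ANCOVA is the wider interval in 66% of trials, though only by 0.727 against 0.724 on average.
- **The scale is borrowed.** The SD of 1.407 comes from the cited study of 5-step infant CPR training, and nothing shows that its skill scale matches this trial's checklists. The ratios carry over; the raw half-widths and the 99.5% hold only on the planning assumptions.
- **The 15+15 split is not documented.** The plan says only that years were equally distributed, and 31 per arm at entry is an odd number. With a 17/13 split the break-even rises to about r = 0.2. Charging chance imbalance for both covariates gives a joint R of about 0.19. Neither changes the advice.
- **Validity is conditional.** Skill is evaluated in pairs, and the document does not say whether pairs were formed within arms. If they were, simulated type I error was 7.3% at a pair intraclass correlation of 0.2 and 11.2% at 0.5. ANCOVA does not cure this (7.4% and 11.0%). It is a separate issue.
- **The text is in the past tense.** If outcomes have been seen, the planned t-test has to stay.

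These points limit the size of the claim. They do not supply the missing time point, and they do not explain why a collected baseline score and the balancing factor are left out.

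**Conclusion.** The concern holds. The plan compares the three outcomes between groups only by an unadjusted t-test without a time point. As regards omitted covariates that test is valid under randomisation, and slightly conservative if year is prognostic. What is given up is precision: with no year effect, about 4% of the standard error at r = 0.3, 13% at r = 0.5 and 28% at r = 0.7, and a little more than nothing is saved below r of about 0.14. For skill at the planned difference the benefit is only a narrower interval. For knowledge and self-efficacy it could be material, with power for an assumed 0.5 SD effect rising from 48% to 59% at r = 0.5. All of this rests on the assumed correlations and on independent students. The point should be fixed because the possible gain is large relative to the possible loss, but it does not undermine the trial.

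**What to change.** State that the between-group comparison is made at post-test. For each of knowledge, skill and self-efficacy, fit an ANCOVA of the post-test score on group, the same instrument's pre-test score and professional year, and report the adjusted mean difference with its 95% CI as the between-group result. Keep the within-arm paired comparisons as description.

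If outcome data have already been seen, keep the planned t-test, state which scores it compared, and report the ANCOVA beside it, labelled post hoc.

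The cost is small. Both covariates are already collected and SPSS 25 fits the model. The price is two degrees of freedom and, if both covariates are nearly uninformative, a trivially wider interval. Dependence within evaluation pairs or teaching groups needs its own treatment.

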negatively due to their training during their undergraduate studies. Since, it is well documented that effective educational programs in preservice settings such as schools of midwifery, nursing, and medicine, established more active forms of lifelong learning to improve the quality of care (Singhal, McMillan, Savich, Matovelo, & Kamath-Rayne, 2020). However, like many other developing countries in Pakistan, the education of nursing students is mostly based on traditional methods that are lacking the component of adequate learning and training in neonatal resuscitation (Huang et al., 2019; Pinar, Akalin, & Abay, 2016), resulting an insufficient knowledge among many trainees on assessment (Huang et al., 2019). Recently, several studies compare traditional methods of educational intervention with integrating new strategies and conclude that new methods are indispensable for nursing education (Kim & Ahn, 2019a; Pinar et al., 2016).

The “Learn, See, Practice, Prove, Do, and Maintain” (LSPPDM) pedagogy is one of such frameworks synthesized after intensely reviewing the literature and acting as a guiding path in teaching and learning of procedural skills (Sawyer et al., 2015). It is augmented that it can impart its role in the improvement of clinical practice resultant to increase patient satisfaction in hospitals (Sawyer et al., 2015). The major goal of LSPPDM pedagogy is to learn a psychomotor skill, accomplishing aptitude, and upholding skill once attained. It is based on adult learning theory that can support the acquisition and maintenance of skills in the area of neonatal resuscitation (Ades & Lee, 2016).

As Knowledge is considering a prerequisite for competence in skill performance and to evaluate the effectiveness of an educational program self -efficacy measurement is an important tool (Mendhi, Premji, Cartmell, Newman, & Pope, 2020). Moreover, a positive relationship is reported between nursing students' knowledge and self-efficacy, both in turn enhancing skill in the

concerned area (Kim & Ahn, 2019b). Thus, the important variables knowledge, self-efficacy, and skill have been selected for this study.

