To the best of researcher knowledge, no published literature was found on this topic in the context of Pakistan. While little published literature is available at the international level. Hence, this was the first study to determine the efficacy of the LSPPDM framework in the teaching and learning of neonatal resuscitation among undergraduate nursing student's knowledge, skill, and self-efficacy conducting at the College of Nursing, Allama Iqbal Medical College, Lahore, Pakistan. The study may provide a groundwork for future trials to investigate the retaining effect that is potentiating through an instructor directing with additional self-directing learning during education.

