## **OBJECTIVES**

The study objective was to:

1. Compare the difference in knowledge among undergraduate nursing students learning of neonatal resuscitation through “Learn, See, Practice, Prove, Do, Maintain pedagogy” as compared to those who had learned through the traditional method.
2. Compare the difference in skill among undergraduate nursing students learning of neonatal resuscitation through “Learn, See, Practice, Prove, Do, Maintain pedagogy” as compared to those who had learned through the traditional method.
3. Compare the difference in self-efficacy among undergraduate nursing students learning of neonatal resuscitation through “Learn, See, Practice, Prove, Do, Maintain pedagogy” as compared to those who had learned through the traditional method.

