## **HYPOTHESIS**

So, the hypothesis was generated as follows:

- a) Hypothesis  $H_0$  a: There is no difference in knowledge among undergraduate nursing students learning of neonatal resuscitation through LSPPDM Pedagogy as compared to those who had learned through the traditional method.
- b) Hypothesis  $H_0$  b: There is no difference in skill among undergraduate nursing students learning of neonatal resuscitation through LSPPDM Pedagogy as compared to those who had learned through the traditional method.
- c) Hypothesis  $H_0$  c: There is no difference in self-efficacy among undergraduate nursing students learning of neonatal resuscitation through LSPPDM Pedagogy as compared to those who had learned through the traditional method.

The alternative hypothesis was as follow:

- a) Hypothesis  $H_1$  a: There is a difference in knowledge among undergraduate nursing students learning of neonatal resuscitation through LSPPDM Pedagogy as compared to those who had learned through the traditional method.
- b) Hypothesis  $H_1$  b: There is a difference in skill among undergraduate nursing students learning of neonatal resuscitation through LSPPDM Pedagogy as compared to those who had learned through the traditional method.
- c) Hypothesis  $H_1$  c: There is a difference in self-efficacy among undergraduate nursing students learning of neonatal resuscitation through LSPPDM Pedagogy as compared to those who had learned through the traditional method.

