## **SAFETY CONSIDERATIONS**

No identified risks associated with this research study; though, a possible inconvenience may be the time it takes to complete the study. Further, it was expounded that the drive of this study is to evaluate the effectiveness of the new educational approach in improving clinical skills in neonatal resuscitation.

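### Do three between-group tests at 0.05 each, with no named primary outcome, call for a multiplicity adjustment?

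*Combined protocol and SAP*

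**What the plan says.** The Objectives section lists three parallel comparisons, one per outcome. The second, for example, is to "Compare the difference in skill among undergraduate nursing students learning of neonatal resuscitation through" the six-step pedagogy rather than the traditional method. The Hypothesis section gives each outcome its own null and its own non-directional alternative; the first null reads "There is no difference in knowledge among undergraduate nursing students learning of neonatal resuscitation through LSPPDM Pedagogy" when compared with the traditional method.

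The Data Analysis Plan handles the three alike: "Independent sample t test was used to compare the mean age, knowledge score, skill score and self-efficacy score between both groups". A single significance rule closes the section: "0.05 was taken as significant".

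No available section uses the terms primary or secondary outcome, orders the tests, adjusts for their number, or says how the three results combine into a verdict on the framework. Three places bear on which outcome leads:

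- **Background.** It presents the outcomes together ("the important variables knowledge, self-efficacy, and skill have been selected for this study") and describes the study as one to "determine the efficacy of the LSPPDM framework in the teaching and learning of neonatal resuscitation among undergraduate nursing student's knowledge, skill, and self-efficacy".
- **Study design and Setting.** The sample size uses skill alone; its inputs begin with "Expected mean in Skill in intervention Group (LSPPDM Pedagogy").
- **Safety Considerations.** It states that "the drive of this study is to evaluate the effectiveness of the new educational approach in improving clinical skills in neonatal resuscitation".

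**The concern.** Three outcomes of apparently equal standing, each tested at 0.05 with nothing named as primary, is the usual pattern behind an inflated false-positive rate. The Background speaks of the efficacy of the framework as a whole, so a reader may fear that one significant score out of three will be reported as proof that the framework works. Under that rule, a framework with no effect on any score would be declared effective more often than the nominal level suggests. The documents do not say that the results will be used this way, but they do not exclude it.

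The natural remedies would be a Holm adjustment across the three tests or the naming of skill as the primary outcome.

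**Working it through.** **Inputs from the documents.** Three outcome comparisons, each two-sided at 0.05 (Hypothesis; Data Analysis Plan). Age is also compared by t-test, but it is a baseline characteristic and is not counted. Planned skill means are 8.71 and 7.03 with SDs 1.48 and 1.33, at 80% power (Study design and Setting). Sixty students completed, 30 per group (Recruitment).

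**Input not in the documents.** The correlation between the scores. The Background reports a positive relationship between knowledge and self-efficacy but gives no size, so a common correlation r from 0 to 0.9 is assumed.

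**1. The plan's own figure.** The normal quantile for 80% power is 0.842.

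n per group = (1.96 + 0.842)² × (1.48² + 1.33²) / 1.68² = 7.85 × 3.959 / 2.822 = 11.01, rounded up to 12.

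This agrees with the stated 12 per group. The plus sign printed between the two brackets of the formula, and the listed quantile of 2.58, do not match that result, but they do not affect the present point.

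**2. Error rate if any one score were enough, all three nulls true.**

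- Independent tests, either direction: 1 − 0.95³ = 0.1426.
- Independent tests, favouring the pedagogy only: 1 − 0.975³ = 0.0731.
- With common correlation r, the rate is 1 minus the probability that all three equicorrelated normal statistics stay inside the limits: |Z| < 1.96 for either direction, Z < 1.96 for one direction.

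| Assumed r | Either direction | Favouring the pedagogy |
|---|---|---|
| 0 | 14.3% | 7.3% |
| 0.5 | 12.5% | 6.3% |
| 0.8 | 9.8% | 4.9% |
| 0.9 | 8.4% | 4.2% |

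Simulated t-tests with 30 per group gave 14.2%, 12.6% and 8.5% for the either-direction rate at r = 0, 0.5 and 0.9, in agreement with the integral.

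A claim of effectiveness needs a difference in favour of the pedagogy, so the right-hand column applies to it. The comparator is 2.5% for one test, not 5%.

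**3. Error rate on the plan as written.** Each null has its own two-sided 0.05 test between groups. A conclusion about knowledge, reported as a conclusion about knowledge, carries 5%, and the same holds for skill and for self-efficacy. The number of other hypotheses does not alter this.

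**4. What Holm would cost at 30 per group.** The planned standardised skill effect is 1.68 / √((1.48² + 1.33²)/2) = 1.68 / 1.407 = 1.194. Skill power is 99.5% at 0.05 and 98.3% at 0.05/3 = 0.0167, the strictest Holm step. The documents give no planned effect for the other two scores. With skill at its planned effect, simulated power for each of them over the full Holm procedure is:

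| Assumed effect (SD) | Unadjusted | Holm |
|---|---|---|
| 0.3 | 21% | 15–16% |
| 0.5 | 48% | 40–41% |
| 0.8 | 86% | 82–84% |

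The loss on skill is negligible. The loss on the other two is not, if their effects are moderate.

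**The case for a change.** The strongest case for a change is that a conclusion about the framework is foreseeable. The Background aims at the efficacy of the framework across all three scores, and the section on expected outcomes speaks of determining the effectiveness of a pedagogical framework and of reinforcing its use. With no rule, such a conclusion could rest on whichever score happened to be significant. One paragraph would prevent that, and no new data would be needed.

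Part of this stands. No primary outcome is designated, and the documents do not say how the results combine. But the aims in the Background and the expected outcomes are general prose, not decision rules. The more concrete statements of purpose point to skill: the sample size rests on it, the Safety Considerations name clinical skills as the drive of the study, and the expected-outcomes text ties effectiveness to resuscitation skills. A reader who wants one lead result has a sensible candidate.

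Nor would the remedies gain much. Holm alone does not say whether one, two or all three adjusted results are needed for an overall claim, so it leaves the combining question open. Naming skill as primary would record a designation that the text already suggests, without altering any test. The Recruitment and Data Analysis Plan sections are in the past tense. If results have been seen, a primary outcome should not be chosen now, and an adjustment would carry only post hoc weight.

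The count of three can also be questioned. Skill is scored on a 30-item technical checklist and a 9-item non-technical scale, and the analysis section does not say whether they are combined. With four tests the either-direction rate would be 18.5% to 9.4% over the same correlations. That enlarges the same hypothetical rate; it does not turn an any-score rule into part of the plan.

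**Conclusion.** The omission is real but minor, and it does not make any planned test invalid. The plan asks three separate questions and answers each at 5%. The inflated rates arise only if someone declares the framework effective because any one score favours it. In that case the false-claim rate would be 7.3% to 4.2% against 2.5% for one test, assuming that all three nulls are true and that the common correlation lies between 0 and 0.9. The documents do not make that declaration.

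Reporting the three differences side by side, each tied to its own hypothesis, is what the Objectives already imply and what a careful analyst would do. Joint control across distinct hypotheses is a convention on which reasonable statisticians differ. Here it would lower power for knowledge and self-efficacy from 48% to about 40% at an assumed 0.5 SD, and it would leave the combining question unanswered. The plan can stand as it is.
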